They will walk for three minutes. If they are comfortable and stable, they will walk an additional 5 minutes at their self-selected walking speed with standby assistance from the principle investigator. Following this ambulation testing, they will then remove the device and liner and re-don the device by themselves. They will then walk for an extended period up to an hour. We will perform gait analysis on selected amputees by placing small reflective markers on their lower body and asking them to walk several times in the Gait and Biomechanics Lab. They will then complete our outcome survey to grade, comfort, fit, ease of use, pain and functionality on an interval scale of 1 to 10. Subjects will grade these domains for the prototype as well as their conventional prosthesis. This testing is safe and of minimal risk. In our early testing with 18 subjects there were no balance losses, skin irritations, or adverse events.

2 Week Home Trial: These participants will be fit with the device by the Principal Investigator and it will be optimally aligned in the laboratory at the Pennsylvania Institute for Rehabilitation (PIRM). They will walk around the building for about 30 minutes in order to insure the fit and alignment are optimal. During this time they will put on and take off the device four times, walk up and down the therapy stairs at the physical therapy department, and perform several sit to stand movements. The participant will need to demonstrate that they can fully utilize the device without the investigators assistance prior to taking it home.

The amputee will be instructed to wear the device as they normally would. They will be asked to refrain from wearing the device during inclement weather (ice or snow), running or highly strenuous activities. Each patient has their own custom prosthesis and should any problems develop, they are to go back to using their conventional device and call the study coordinator. For new amputees without a conventional prosthesis, we will give them some gait training during their first visit. They will then be instructed to bring the prosthesis to physical therapy to continue training with it.

They will be given the phone number of both the Principal Investigator, [name], and the Research Coordinator, [name], to report any issues with the device. The participant will be contacted after the first 24 hours, and again after the first week by the Research Coordinator to assess their progress and record any issues.

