2 Week Follow Up: The participant will return two weeks following the initial fitting. They will fill out the PEQ – based outcome questionnaire again on the iFIT socket. They will complete a gait analysis wearing the iFIT Prosthesis as well as their conventional prosthesis. They will also have socket internal pressure measurements taken using Fuji-film prescale. This will be placed in five locations on top of the silicone liner: anterior proximal, anterior distal, lateral, medial and posterior. They will ambulate in the lab for two minutes and then have the papers removed for analysis. This will be completed on both sockets. The PI will also inspect the participant's skin for limb ischemia, edema, redness or skin breakdown. The socket will also be inspected for any wear or mechanical breakdown.

Data Storage:

All data on paper is kept in a locked filing cabinet which is accessed only by the Research Coordinator. Computer files are kept on PC's managed by Penn Medicine Academic Computing Services (PMACS). Key study personnel other than the Research Coordinator ensured data collected through questionnaires and Fujifilm was valid and correct. All data for analysis is de-identified prior to sending to the statistician for analysis.

Transtibial Statistical Analysis Plan:

Standard summary statistics, such as mean and SD or frequency and percentage were used to describe the study population. To test for differences in questionnaire score and pressure data between prosthetic devices, paired t-tests were used. For the questionnaire score analyses, two separate paired t-tests were performed.

One for participants with a complete set of questionnaire scores; another used an intention to treat analysis that included the 4 noncompleters with no questionnaire scores at 2 weeks for the iFIT device. For this latter analysis, it was assumed that the

non-completers would have worse scores on the iFIT device than reported with their conventional device at the first visit. Therefore, to impute a value for the iFIT device, the mean difference between devices (own vs iFIT) for the participants who completed testing ($n = 22$) were subtracted from the scoring for the noncompleters regarding their conventional devices at the first visit. This modeled a worse-case scenario (less satisfaction) with the iFIT device compared

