to the conventional device for people who dropped out. To test for differences between prosthetic devices for the gait biomechanical measures, a single-group 2-way analysis of variance with repeated measures, where leg (involved, unininvolved) and device (own, iFIT) were the repeated measures. All analyses were performed using SAS statistical software (version 9.4, SAS Institute, Cary, NC).

Transfemoral Statistical Analysis Plan:

A sample size of 12 to 14 was predicted to achieve $>80\%$ power, with an alpha of 0.05, using a clinically meaningful difference of 1 (effect size) on an individual PCUQ question (range of score, 1-5) with SD of the mean difference as large as 1.3. To describe the study population, frequencies and percentages were calculated for categorical variables, and means and standard deviations were calculated for continuous variables. To compare responses to the individual PCUQ questions and the patient satisfaction score between the iFIT device and patients' conventional device, paired t-tests were used because the mean differences were approximately normally distributed, with only mild left skew and lightly tailed. Results are presented as mean difference 95% confidence intervals between the adjustable socket and the conventional device. All analyses were performed using SAS statistical software (version 9.4, SAS Institute, Cary, NC). Data were collected by the study coordinator and maintained by her independent of the principal investigator. All statistical analyzes were performed by the biostatistician ([name]) independent of the principal investigator.

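### The transtibial dropout imputation leaves its sign unstated and fixes the non-completers' deficit from the completers' own result, so it cannot test robustness to dropout

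*Combined protocol and SAP*

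**What the plan says.** The Transtibial Statistical Analysis Plan describes two paired t-tests on the questionnaire scores. One uses participants with complete scores. The other, called intention to treat, adds the 4 non-completers who have no 2-week iFIT score. Its premise is that "non-completers would have worse scores on the iFIT device than reported with their conventional device at the first visit". The amount used is "the mean difference between devices (own vs iFIT) for the participants who completed testing", of whom there were 22, and these differences "were subtracted from the scoring for the noncompleters regarding their conventional devices at the first visit". The plan then characterises the result: "This modeled a worse-case scenario (less satisfaction) with the iFIT device compared" "to the conventional device for people who dropped out".

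The plan does not say which device's score is taken from which, whether imputed values are held within the scale, or whether the variance is adjusted for imputation. It tries no other size of deficit and describes no other analysis that addresses dropout.

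**The concern.** An analysis of dropout should show whether the conclusion survives if those who left fared worse than those who stayed. Here the assumed deficit is taken from the completers' result, so a small completer difference implies a small assumed deficit. The wording also allows two signs with opposite consequences: one copies the completers' effect to the dropouts, the other reverses it. Finally, an ordinary t-test treats the filled-in values as if they had been observed.

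Dropout could well be related to satisfaction. The 2 Week Home Trial section tells participants to return to their conventional device if problems develop. The 4 non-completers are 4/26 = 15.4% of the group analysed.

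**Working it through.** **Inputs.** The 22 completers and 4 non-completers come from the Transtibial SAP; 26 is their sum. Two-sided 0.05 is assumed, because an alpha of 0.05 is given only in the Transfemoral SAP. The completers' mean m and SD s of (iFIT minus own) are not given, so results are expressed through r = m/s. Further assumptions:
- Higher scores are better. The 2 Week Follow Up describes a PEQ-"based outcome questionnaire again on the iFIT socket" without range or direction. The 1-to-10 range belongs to the in-lab survey under Procedures.
- Imputed values are not truncated.
- All 4 have own-device scores. The 2 Week Home Trial also provides "For new amputees without a conventional prosthesis", but the rule treats first-visit conventional scores as available.

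The transtibial plan states no power, effect size or p-value, so there is no figure to reproduce.

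**Step 1: the imputed paired difference.** Let x be a non-completer's own-device score.
- Reading A (own minus iFIT): imputed iFIT = x − (−m) = x + m, so the paired difference is +m.
- Reading B (iFIT minus own): imputed iFIT = x − m, so the paired difference is −m.

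In both, x cancels and the four paired differences are one repeated number.

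**Step 2: reading A.**
- Mean = (22m + 4m)/26 = m, and the sum of squares stays at 21s².
- SE relative to completers = √(21/25) × √(22/26) = 0.843, so t is multiplied by 1/0.843 = 1.186.
- Completer p = 0.050 means t = 2.080 on 21 df. This becomes 2.080 × 1.186 = 2.467 on 25 df, p = 0.021.
- The 25-df critical value is 2.060. Dividing by 1.186 gives a completer t of about 1.74, p = 0.097. Null rejection is therefore about 9.7%.

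**Step 3: reading B.**
- Mean = (22m − 4m)/26 = 18m/26 = 0.692m.
- Sum of squares = 21s² + 22(8m/26)² + 4(44m/26)² = 21s² + 13.54m².
- t = 0.692r / √[(21 + 13.54r²)/(25 × 26)].
- At completer p = 0.050, r = 2.080/√22 = 0.443. The mean is 0.307s, the SE is √(23.66/650) s = 0.191s, t = 1.609 and p = 0.120.
- Significance needs r of at least 0.592, a completer p of about 0.0113. Null rejection is therefore about 1.1%.

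**Step 4: what reading B cannot show.**
- A zero mean needs 22m + 4c = 0, so c = −5.5m. The rule fixes c = −m, so the mean can neither reach zero nor change sign.
- If completers rated iFIT worse (m < 0), −m is positive and the dropouts are imputed as preferring iFIT.
- The imputed deficit equals r in completer SDs: 0.81 at completer p = 0.001, 0.60 at 0.01, 0.44 at 0.05, 0.28 at 0.20 and 0.15 at 0.50.
- In 200,000 simulated trials per setting, with dropouts truly at −5.5 times the completer mean (true 26-person mean zero), reading B still rejected in 36%, 69% and 96% at true completer r of 0.5, 0.7 and 1.0.

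**Step 5: what a tipping-point analysis would show.** Use a normal model without predictors, add a shift delta to the imputed differences, and combine by Rubin's rules in the limit of many imputations. The pooled mean is m + (4/26)delta. The conclusion tips at delta = −0.87, −0.51, −0.27 and −0.09 completer SDs for completer p = 0.01, 0.02, 0.03 and 0.04. At p = 0.01 the dropouts' implied mean at tipping is 0.60 − 0.87, about a quarter of an SD below their own device. The planned analysis cannot produce that statement.

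**The case against.** The best defence is that the text points to reading B. The plan assumes worse iFIT scores, subtracts for that reason, and reports less satisfaction. Where completers favoured iFIT, that means a positive amount taken off. Reading B then lowers the mean by 31% and is conservative under the null, so it does not manufacture an iFIT benefit. This stands, and the 9.7% figure must not be presented as what the trial did: the documents do not show which sign was used. It does not answer the main point, since conservatism when every true difference is zero is not robustness to dropouts who fared badly.

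Four stronger readings are tempting but unsupported:
- *The plan claims a worst case and fails to deliver it.* The plan says worse-case, and the sentence reads as worse than the person's own device. The fair criticism is that the scenario is a single deficit and does not bound the result.
- *The reported standard error is about 15% too small.* That holds only against multiple imputation with delta fixed at −2m, where the ratio is 0.845 at completer p = 0.05 and 0.872 at 0.001. The repeated-sampling SE of the estimator 0.692m is 0.692 × s/√22 = 0.148s, below the 0.191s that reading B reports at p = 0.05. The choice of variance is a methodological one, not a demonstrated error.
- *The absolute difference may have been subtracted.* Nothing in the text suggests it.
- *Subtraction may have improved a pain score.* Pain is named in the in-lab survey ("grade, comfort, fit, ease of use, pain and functionality on an interval scale of 1 to 10"), but the documents do not list it in the 2-week questionnaire.

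It is also fair that only 4 people are affected and that the completer test is reported separately. That limits the weight of the point without removing it.

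**Conclusion.** The concern holds in this limited form. The rule leaves its sign unstated. Read as own minus iFIT, it contradicts the plan's own assumption wherever completers favoured iFIT and makes p-values too small (0.050 becomes 0.021). Read the other way, it is conservative under the null (0.050 becomes 0.120), yet it fixes the 26-person mean at 18/26 of the completer mean and goes against the assumption wherever completers rated iFIT worse. Under either sign the four paired differences carry no imputation uncertainty and the result follows from the completers alone. The only stated dropout analysis therefore cannot say how much worse dropouts would have to rate iFIT before a conclusion changes.

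The structural points need only 22 and 4, no truncation, and own-device scores for all 4. The p-values also assume a two-sided test at 0.05, and the null rejection rates assume normal differences. The documents do not establish that any reported result is wrong or in which direction it errs. This should be fixed but is not fatal, because the completer test does not depend on it.

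**What to change.** 1. State the imputation formula, the sign actually used (it can be read from the analysis program) and any truncation to the scale.
2. Describe the scenario as one assumed deficit, not a bound.
3. Replace it as the dropout sensitivity analysis, or supplement it, with a delta-adjusted multiple-imputation analysis of the iFIT-minus-own difference. Set the deltas in scale points, independently of the completers' mean and in the unfavourable direction for each score. Combine by Rubin's rules and report the delta at which each conclusion changes.
4. State the range and scoring direction of each score, and how many of the 4 had own-device scores.
5. Optionally, add a bound that sets each missing iFIT score to the least favourable scale value, labelled as extreme and not as plausible.

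The cost is SAP wording and a rerun on existing data. At the same assumed deficit, the interval will be wider than the constant imputation reports: at completer p = 0.010, reading B gives p = 0.047 and multiple imputation with the same deficit gives 0.088. Depending on the deltas chosen, the estimate may be more or less favourable to iFIT than the current one.

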**Immediate Fit Using Innovative Technology Transtibial & Transfemoral
Prostheses**

iFIT Prosthetics, LLC

May 13, 2022

NCT02886936

Transtibial Device Testing Protocol

Location: Penn Medicine Department of PM&R Gait Lab

PI: [name], MS, MD

Research Coordinator: [name], MS

Funding: National Institutes of Health, National Institute on Aging (grant nos. 2SB1AG050430-06 and 2R42AG050430-04) and the National Institute of Child Health and Human Development and National Center for Medical Rehabilitation Research (grant nos. 2R42 HD069067-02 and 1R41HD069067-01).

Overview: Persons with limb loss were recruited for a two week home trial to test out an immediate fit, adjustable, lower limb prosthesis.

Key inclusion criteria:

i) transtibial level of amputation, ii) ambulate with or without a gait assistive device or has the potential to ambulate with gait assistive device if this is their first prosthesis, iii) has been cleared by surgeon to be fit with prosthesis or is already wearing prosthetic device. We will include persons with limb loss due to cancer (very rare), trauma, and dysvascular causes (diabetes).

Key exclusion criteria:

Subjects will be excluded if; i) they have skin ulcerations on the residual limb, ii) have other central nervous system disorders such as strokes and brain injuries that interfere with safe ambulation and gait testing, or iii) severe phantom or limb pain.

Procedures:

Full informed consent for all subjects will be obtained. If an adolescent participates, consent will be obtained from both the parent and the child. Participation will take approximately 3.0 hours and will be conducted in one of our outpatient therapy areas. Subjects, after signing an informed consent, will be fit with the prototype device that uses a buckle system and easily adjusts to conform to the residual limb and provide optimal alignment. The principal investigator ([name]) who lead the Phase I study and who has considerable clinical experience in optimally aligning the device, will fit and test all subjects. The optimal height will be achieved by using the proper size of shank connector (multiple length connectors for the foot are precut) and all subjects will use a SACH foot with their current shoes. Subjects will then ambulate on a flat open surface with the principal investigator providing contact guard with a safety waistbelt.

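### Does the transtibial gait ANOVA hide a change in the fitted leg by averaging it with the other leg?

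*Combined protocol and SAP*

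**What the plan says.** In the Transtibial Statistical Analysis Plan the gait model is introduced with "To test for differences between prosthetic devices for the gait biomechanical measures, a single-group 2-way analysis of variance with repeated measures" and its factors are given as "where leg (involved, unininvolved) and device (own, iFIT) were the repeated measures". The section does not name the term that answers the device question. It gives no rule for a leg-by-device interaction, no gait estimate or interval, and no list of gait measures.

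For the other transtibial outcomes the same section says: "To test for differences in questionnaire score and pressure data between prosthetic devices, paired t-tests were used". Under 2 Week Follow Up, the pressure film is described with "This will be placed in five locations on top of the silicone liner" and then "This will be completed on both sockets". Gait is recorded with each prosthesis at that visit.

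Under Procedures, the prototype is described as one that "easily adjusts to conform to the residual limb and provide optimal alignment". That the uninvolved leg wears no prosthesis is a reasonable inference from this and from the factor labels; it is not stated in words.

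**The concern.** The aim is a comparison of devices, so the natural reading is that the device main effect is the test. That term weights both legs equally, although only one carries the device. A reader who takes it as the change in the fitted leg may see a diluted figure. If the legs respond in opposite directions, a non-significant result could be taken as evidence that the devices do not differ in gait.

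The paired t-test on pressure adds to the impression. There, a device difference plainly belongs to the fitted limb, while almost the same words for gait seem to mean a two-leg average. At stake is the meaning of every per-leg gait result.

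**Working it through.** **Inputs.** The 2 × 2 within-person structure comes from the Transtibial Statistical Analysis Plan. The documents give no gait sample size, SD, between-leg correlation, effect size or transtibial alpha, so there is no stated figure to reproduce.

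**1. What each term estimates.** Let D and U be the mean iFIT-minus-own differences in the involved and uninvolved leg.

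- Device main effect: M = (D + U)/2
- Leg-by-device interaction: I = D − U
- Hence D = M + I/2 and U = M − I/2

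As percentages of D:

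| U/D | M | I | M + I/2 |
|---|---|---|---|
| 1 | 100 | 0 | 100 |
| 0.5 | 75 | 50 | 100 |
| 0 | 50 | 100 | 100 |
| −0.5 | 25 | 150 | 100 |
| −1 | 0 | 200 | 100 |

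The dilution in the M column is real. The last column shows that the same model recovers the involved-leg difference in full.

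**2. Numerical check.** One simulated data set of 22 people was analysed by two-way repeated-measures ANOVA. The device F(1,21) was 3.5772 (p = 0.0725), identical to the squared paired t on the leg-averaged differences. The leg differences were D = 0.5850 and U = 0.0418.

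- M = (0.5850 + 0.0418)/2 = 0.3134
- I = 0.5850 − 0.0418 = 0.5432
- M + I/2 = 0.3134 + 0.2716 = 0.5850

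The ANOVA table had three lines: leg, device, and leg by device (F = 2.0663, p = 0.1653).

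**3. Is the average a worse target?** Assume equal SD s of the device difference in both legs, between-leg correlation r, and U = kD. The signal-to-noise ratio of each term, relative to an involved-leg paired contrast, is:

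- main effect: (1 + k)/√(2(1 + r))
- interaction: (1 − k)/√(2(1 − r))

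These do not depend on sample size. Over an assumed range of r:

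| r | Main, k = 1 | Main, k = 0 | Interaction, k = 0 | Interaction, k = −1 |
|---|---|---|---|---|
| −0.5 | 2.00 | 1.00 | 0.58 | 1.15 |
| 0 | 1.41 | 0.71 | 0.71 | 1.41 |
| 0.5 | 1.15 | 0.58 | 1.00 | 2.00 |
| 0.8 | 1.05 | 0.53 | 1.58 | 3.16 |

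The main effect beats the involved-leg contrast when k exceeds √(2(1 + r)) − 1, which is 0, 0.41, 0.73 and 0.90 for the four values of r. Below that it does worse. At k = −1, where the main effect is blind, the interaction is more sensitive than the involved-leg contrast at every r shown. At k = 0 the better of the two terms is never below 0.71. No choice wins throughout.

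**4. Pressure beside gait.** The film lies between liner and socket, so socket pressure exists only on the fitted limb, and a paired t-test is the only sensible form. Gait is measured on both legs, and the plan makes leg a factor. Different outcomes call for different contrasts; this is not a contradiction.

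**5. Why no power figure is offered.** The phrase "We will perform gait analysis on selected amputees" stands in the Procedures account of the fitting session, and no gait count appears anywhere. The 22 completers, and the analysis that "included the 4 noncompleters with no questionnaire scores at 2 weeks for the iFIT device", are described through the questionnaire. The number 22 is therefore not a supported bound for gait, and a power statement would rest wholly on assumed inputs.

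**The case for a change.** The strongest case for acting is that the silence is real and cheap to end. One sentence does not say which term is the test, and the algebra shows that the obvious choice can halve or cancel a change in the leg that matters. The transfemoral plan does name its estimate and interval, so the authors knew how. Giving both leg-specific differences needs no new data.

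The algebra and the silence both stand, and leg-specific differences would help a reader. The rest is weaker. The harm needs a report that shows the device line, omits the interaction, and reads a non-significant average as equality; the plan prescribes none of these. Replacing the average by the involved-leg contrast changes the question asked. A prosthesis can alter the gait of the other leg, so the average is a legitimate device effect. A rule for when an interaction counts as present would need its own threshold. It would also be set after the data, because the section already cites completers and noncompleters, so it could not restore pre-specification. For a whole-body measure such as walking speed the leg factor does not arise at all.

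**Conclusion.** The concern does not call for a change. The device main effect equals the involved-leg change only when both legs change alike, but the model is sound. Its interaction covers the cases where the average misleads, and the two terms together give each leg's difference exactly. What is missing is a sentence on reading and reporting a standard two-way table, which a competent analyst supplies. Labelling a main effect as an average over both legs, or showing the legs separately, is a choice for the report.

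The possible dilution runs from 0 to 100% of the involved-leg change as U/D goes from 1 to −1. Where this trial falls is unknown, and neither direction of advantage is established. The conclusion rests on three assumptions: the interaction was fitted, as is conventional for the named model; the uninvolved leg carries no prosthesis; and the measures concerned are recorded per leg. If the interaction had been left out of the fitted model, the point would carry more weight, but nothing in the documents says so.

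### Transfemoral sample size: 12 to 14 participants give 68% to 76% power for a two-sided paired t-test, not the stated >80%

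*Combined protocol and SAP*

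**What the plan says.** The sample-size statement opens the Transfemoral Statistical Analysis Plan: "A sample size of 12 to 14 was predicted to achieve" power above 80%, "with an alpha of 0.05". The target is a raw difference of 1 point on a single PCUQ item scored 1 to 5, labelled an effect size, "with SD of the mean difference as large as 1.3". The same section names the analysis: "paired t-tests were used because the mean differences were approximately normally distributed". It then describes the reporting: "Results are presented as mean difference 95% confidence intervals between the adjustable socket and the conventional device".

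The section does not say whether alpha is one- or two-sided. It also does not say whether 12 to 14 counts enrolled participants or complete pairs. The documents contain no other power statement; the Transtibial Statistical Analysis Plan has none.

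**The concern.** A difference of 1 with an SD of 1.3 is a standardised effect of 1/1.3 = 0.77. For a two-sided paired t-test at the 5% level, 12 to 14 pairs looks too few for 80% power at that effect. Two-sided is the natural reading, because the comparison between devices is given no direction and a 95% confidence interval corresponds to a two-sided 5% test.

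This figure is the only justification given for the transfemoral sample size. If it is too high, the study is more likely than stated to miss a difference that the plan itself calls clinically meaningful, and a reader weighing a non-significant PCUQ item would credit the comparison with more sensitivity than it has.

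**Working it through.** **Inputs, all from the Transfemoral Statistical Analysis Plan:** n = 12 to 14; difference 1; SD of the paired differences 1.3 (the stated upper limit); alpha 0.05; paired t-test. Only the sidedness has to be inferred.

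**Formula.** The test statistic follows a noncentral t distribution with df = n − 1 and noncentrality λ = √n × (1/1.3). Two-sided power is P(T > c) + P(T < −c), where c is the 97.5% point of the central t. One-sided power is P(T > c₁), where c₁ is the 95% point.

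**Reproducing the plan's figure.** With one-sided alpha 0.05, n=12 has λ = 3.464/1.3 = 2.665 and c₁ = 1.796, giving 80.3%. Twelve is the smallest n that reaches 80% on this basis, and every n from 12 to 14 exceeds it. So the stated range and power fit a one-sided calculation.

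**Two-sided, matching the 95% intervals:**

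| n | λ | c (two-sided) | Two-sided t | One-sided t | Two-sided normal approximation |
|---|---|---|---|---|---|
| 12 | 2.665 | 2.201 | 68.0% | 80.3% | 76.0% |
| 13 | 2.774 | 2.179 | 72.1% | 83.3% | 79.2% |
| 14 | 2.878 | 2.160 | 75.8% | 86.0% | 82.1% |
| 15 | 2.979 | 2.145 | 79.1% | 88.2% | 84.6% |
| 16 | 3.077 | 2.131 | 82.0% | 90.1% | 86.8% |

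The normal approximation is Φ(λ − 1.96). It exceeds 80% at n=14 but not at 12 or 13. At these sample sizes it overstates the t-test's power by about 6 to 8 points (82.1 − 75.8 = 6.3 at n=14; 76.0 − 68.0 = 8.0 at n=12).

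**What would give 80% two-sided:**
- With a difference of 1, the SD may be at most about 1.12 (n=12), 1.18 (n=13) or 1.23 (n=14). All are below 1.3.
- With SD 1.3, the true difference must be about 1.16 (n=12) or 1.05 (n=14).

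**Sensitivity to loss (an assumption).** The transfemoral section gives no loss rate. The transtibial section reports 4 noncompleters and 22 completers, so 4/26 = 15%. If the same proportion applied here, 12 × 22/26 = 10.2 and 14 × 22/26 = 11.8, or about 10 to 12 pairs. Two-sided power is then 58.3% at n=10 and 68.0% at n=12.

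**The case against.** The strongest reply is that the arithmetic may be right and only the label missing. The plan gives alpha as 0.05 without a side, the one-sided calculation reproduces the claim at every n in the range, and 12 is exactly its smallest qualifying n. The interval sentence describes reporting, not necessarily the design alpha. It stands that two-sidedness is an inference. But no directional hypothesis or one-sided bound appears anywhere in the documents, so even if this reading is right the power statement does not describe the comparison as reported.

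A second reply is that 12 to 14 tracks a range of SDs, with 14 meant for SD 1.3. Under the two-sided normal approximation that works: n=14 covers SD up to about 1.34 and n=12 up to about 1.24. The text pairs no n with any SD, however, and the planned t-test still gives only 75.8% at n=14.

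A third reading takes the effect-size label literally as a standardised effect of 1. Two-sided power would then be 88% to 93%, but the stated SD of 1.3 would have no role, and the text ties the 1 to a 1-to-5 score.

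On importance, it is fair to say that the section is written in the past tense, that correcting it changes no estimate, interval or p-value, and that reporting intervals limits over-reading of a null result. The 24% to 32% miss rate applies at the upper-limit SD; at an SD of 1.12 or less, 80% is reached even with 12 pairs. The loss calculation is borrowed from another cohort and is not part of the error. These points limit the consequences but leave the stated figure wrong.

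**Conclusion.** The concern holds. With the plan's own difference, SD and alpha, a two-sided paired t-test has 68.0% to 75.8% power at n = 12 to 14. That is at least 4 points short of 80% at n=14 and 12 points short at n=12, and 16 pairs are needed to pass it. The probability of missing a true 1-point difference at SD 1.3 is 24% to 32%.

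This rests on two assumptions: that the test is two-sided, as the 95% intervals and the undirected comparison indicate, and that 12 to 14 counts complete pairs. If the number includes participants who cannot supply both ratings, power is lower. If a one-sided test was used for planning, the figure is reproducible but the plan does not disclose it and its intervals do not match it.

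**What to change.** State the sidedness and the method used for the calculation. For the two-sided test, replace the power sentence with:

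*With 12 to 14 participants contributing complete pairs, a two-sided paired t-test at alpha 0.05 has 68% to 76% power to detect a difference of 1 point (standardised effect 0.77) on an individual PCUQ question if the SD of the differences is 1.3. Power of 80% holds for an SD up to 1.12 (n=12) or 1.23 (n=14).*

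This wording also removes the effect-size label from the raw difference. If planning was in fact one-sided, say so, justify it, and still give the two-sided power beside the 95% intervals.

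The cost is a short rewording in the SAP and a less favourable stated power. No extra patients and no change of analysis are needed.

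### Does the transfemoral plan need a named primary outcome or a multiplicity adjustment for its PCUQ comparisons?

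*Combined protocol and SAP*

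**What the plan says.** All of this is in the Transfemoral Statistical Analysis Plan. The sample size of 12 to 14 is set "with an alpha of 0.05" and power above 80%, for a "difference of 1 (effect size) on an individual PCUQ question", with an SD of the paired difference of up to 1.3. No item is named.

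The analysis sentence then covers a set of outcomes. Paired t-tests are used "To compare responses to the individual PCUQ questions and the patient satisfaction score between the iFIT device" and the patient's own device. On reporting, the section says: "Results are presented as mean difference 95% confidence intervals between the adjustable socket and the conventional device".

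Neither this section nor the rest of the document names a primary outcome, counts the PCUQ items, orders the tests, adjusts for their number or calls the item results exploratory. Nor does the section state a family-wise error rate, a success criterion, or a rule that turns a significant item into a claim about the device.

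**The concern.** An alpha, a power target and a clinically meaningful difference are the furniture of a confirmatory test, and such a test needs a stated hypothesis. Here the calculation is for one item, while the analysis covers several items and a satisfaction score. If each comparison is read at 0.05, which the single alpha and the 95% intervals suggest, the chance of some false positive across the set exceeds 0.05.

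At stake is how an isolated favourable item is read. With 12 to 14 participants and an unlisted set of outcomes, a reader who sees one interval excluding zero cannot tell from the plan how many others could have done so by chance.

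**Working it through.** **Inputs.** From the Transfemoral Statistical Analysis Plan: n = 12 to 14, alpha 0.05, difference 1, SD of the difference up to 1.3, paired t-test, 95% intervals. Not given: sidedness, the number of tests k, and the correlation between outcomes. Two or more items plus the satisfaction score give k of at least 3. The values k = 6 and k = 10 and all correlations are assumptions.

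**1. The plan's own sample size.** The standardised difference is d = 1/1.3 = 0.769. The noncentrality is d√n, which is 0.769 × 3.464 = 2.66 at n = 12 and 0.769 × 3.742 = 2.88 at n = 14.

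| Method, single test at 0.05 | Power, n = 12 | Power, n = 14 | n for 80% |
|---|---|---|---|
| Paired t, one-sided | 80.3% | 86.0% | 12 |
| Normal approximation, two-sided | 76.0% | 82.1% | 14 |
| Paired t, two-sided | 68.0% | 75.8% | 16 |

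The normal approximation is ((1.960 + 0.842) × 1.3)² = 13.26, rounded up to 14. The full range of 12 to 14 is reproduced by a one-sided test, and its upper end by the two-sided approximation. In every case the figure is for one test with no adjustment. Sidedness is a separate matter, noted here because the power figures depend on it.

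**2. Chance of at least one false positive.** With independent tests and no true differences it is 1 − 0.95^k. For k = 3 that is 1 − 0.857 = 14.3%, for k = 6 it is 26.5%, and for k = 10 it is 40.1%. Simulation (two-sided 0.05, n = 13, equally correlated normal differences, 100,000 runs) gives:

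| k | Correlation 0 | 0.5 | 0.9 |
|---|---|---|---|
| 3 | 14.3% | 13.0% | 8.6% |
| 6 | 26.6% | 21.5% | 11.3% |
| 10 | 39.8% | 30.0% | 13.6% |

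Only the first row rests on the plan's wording. The 40% figure needs ten independent outcomes rated by the same 12 to 14 people.

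**3. Chance of two or more false positives.** For k = 3 and independent tests: 3 × 0.05² × 0.95 + 0.05³ = 0.7%. Over correlations 0 to 0.9 (n = 13, 20,000 runs) the range is 0.7 to 4.3% for k = 3, 3.3 to 6.7% for k = 6 and 8.6 to 10.8% for k = 10. At the family size the text implies, two chance findings together stay below 5%.

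**4. What adjustment would cost.** Power per item at difference 1 and SD 1.3, n = 12 to 14. The Bonferroni figure (alpha/k) is the floor under Holm.

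| Tests | Two-sided | One-sided |
|---|---|---|
| Unadjusted | 68–76% | 80–86% |
| k = 3 | 47–57% | 60–69% |
| k = 6 | 35–44% | 47–57% |
| k = 10 | 27–36% | 38–48% |

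If every outcome truly differs by that amount, two-sided Holm power per item is about 55–67%, 44–56% and 33–48% for k = 3, 6 and 10.

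**5. What each possible change would do.**

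- *Label the results descriptive.* The estimates and 95% intervals stay as they are. The coverage of any one interval does not depend on how many others are reported.
- *Name a primary outcome.* The section already reports the data, saying "the mean differences were approximately normally distributed, with only mild left skew and lightly tailed". A primary outcome chosen after that point would be post hoc and would protect nothing, unless earlier records support it.
- *Apply Holm.* Family-wise error falls to 2 to 5% in the settings of step 2, at the cost shown in step 4.

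**The case for a change.** The strongest case for a change is that the plan borrows confirmatory language and then leaves the family open. It states an alpha, a power target and t-tests, yet gives no list of items and no rule for a mixed result. Any item below 0.05 could later be presented as the one the study was sized for. Even at three tests and correlation 0.9 the chance of some false positive is 8.6%, above 0.05, and one sentence would settle how the results are to be read.

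The facts in this stand: no primary outcome, no count of items and no multiplicity statement appear anywhere, and the arithmetic is right. The inference is weaker. The calculation refers to any one item: it uses an indefinite article, the score range common to the items, and an upper bound on the SD where a particular item would have its own value. On that reading no special item was left unnamed, and the 0.05 is a per-item rate used as stated. Because the section makes no family-wise promise, a family-wise rate above 0.05 contradicts nothing in it. The request for a sentence is fair as a matter of presentation, but it would leave the analysis and every number unchanged.

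**Conclusion.** No change is needed. The plan describes a small single-group comparison of two devices, sized per item and reported as mean differences with 95% intervals. Each interval stands on its own, and no stated property of the design is shown to be false.

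The size of the issue that the text supports is a 9 to 14% chance of at least one false positive. That assumes three tests, two-sided 0.05, n = 13, no true differences, and correlation from 0.9 down to 0. Larger figures rest on family sizes the document does not give.

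The unlisted items are a gap that an analyst fills by reporting every PCUQ item and the satisfaction score side by side, so that readers can count the intervals. Whether to adjust across questionnaire items at this sample size is a trade-off on which reasonable statisticians differ. With three tests, two-sided power per item could fall from 68–76% to as low as 47–57%. The conclusion would be different if the plan tied a device claim to any one significant item, and it does not.
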